Transcutaneous Electrical Nerve Stimulation of Penile Nerves for Treatment of Delayed Ejaculation

Study Protocol

NCT04115540

April 19, 2021

Scientific Protocol

1) Name of study

Transcutaneous electrical stimulation of the penile nerves for delayed ejaculation

2) PI and other key investigators or key study personnel

[name] (PI) and [name]

3) Specific source of institutional funding (account number)

No institutional funding

4) List of sources from whom you are seeking funds (or have sought funding) for this project

Urology Department, Stanford University School of Medicine

5) Specific aims and basic hypothesis including an explicit primary hypothesis or goal

The aim of this clinical trial is to test the safety and feasibility of using transcutaneous electrical nerve stimulation of the penile nerves to reduce ejaculatory latency in men with delayed ejaculation. We hypothesize that this type of stimulation, either before or during sexual activity, will reduce ejaculatory latency time.

6) General background (2 page maximum including published preclinical and animal data supporting basic hypothesis, if relevant)

Delayed ejaculation (DE) is a condition in which men suffer a delay of intravaginal ejaculatory latency time (IELT) of more than 21-23 minutes.¹ Due to variations in definition and inherent difficulty in characterizing the prevalence of the condition, the epidemiology is varied.

However, the prevalence ranges in the literature from about 1-4% with the true incidence believed to be higher.^{1,2} Current treatment for DE is either counseling or off label pharmaceuticals. Counseling generally involves addressing a known underlying psychogenic cause and can involve such interventions as cognitive behavioral therapy, sex therapy, or psychotherapy.³ However, these techniques can offer be time consuming and their efficacy varies greatly. Off label medications are the only current pharmacotherapy available for the treatment of DE. Various medications have been used off-label such as ephedrine, bupropion, and oxytocin. While some of these medications improve IELT, they remain cumbersome as they are daily medications and have potential serious adverse side effects.^{2,3}

There are currently no devices on the market for treatment of DE, however the anatomy of the penis allows for potential intervention. The main nerves to the penis branch off the pudendal nerve and provided sensory innervation allowing for stimulation and therefore are a potential target for treatment of DE. We therefore hypothesize that transcutaneous electrical stimulation of the nerves of the penis, either before or during sexual activity, may improve IELT. While there have been no animal or human studies in the literature looking at DE specifically, transcutaneous stimulation of branches of the pudendal nerve to treat a variety of urologic conditions has been done in the past. Laessoe et al demonstrated that transcutaneous vibratory stimulation of the penis can induce ejaculation as well as reduce detrusor overactivity within the bladder while Sonksen et al showed that perineal transcutaneous electrical stimulation can treat stress urinary incontinence.^{4,5} Transcutaneous penile nerve stimulation through vibration was shown in 66 patients with spinal cord injury to be successful in inducing ejaculation.⁶ Finally, Fode et al found in post-prostatectomy patients that transcutaneous penile nerve stimulation with vibration may be helpful in improving erectile function.⁷ While none of these studies examined DE specifically, they do demonstrated that transcutaneous stimulation of the penile nerves, or more proximal branches, can lead to observable effects within the structures they innervate which can be applied in treatment of DE.

7) Preliminary unpublished data (1 page maximum)

We performed a pilot study using a transcutaneous electric nerve stimulator (TENS 7000) with TENS pads applied directly to the penis in men with delayed orgasm. The study enrolled 14 men who wore the device during intercourse, before intercourse, and daily in serial fashion for 6 weeks each. Men completed validated questionnaires regarding sexual function as well as questions regarding device use/comfort. Approximately 40% of men reported subjective improvement with mean scores on intercourse and overall satisfaction showing increases. However, 64% of men reported problems with using the TENS pads on the penis which limited use.

Using the feedback, we designed a unique wearable to continue this project based. The device use similar technology to other devices available online for neurostimulation of the penis. The device is connected to the TENS unit leads and uses conductive rubber to apply current directly to the skin. Instead of TENS pads there are two sets of conductive rubber tubes which pass current to stimulate penile nerves. The devices uses an elastic system to fit securely on the penis and deliver TENS stimulation. Men are provided guidance to use a similar range of stimulation parameters (e.g. Amplitude, voltage, frequency, pattern) to the TENS pad pilot study. The size of the device will prevent most men from using the device during intercourse. Rather the device will be used either before sex or daily (2 arms to the next proposed pilot study).

8) Experimental design and data analysis, including inclusion and exclusion criteria, statistical basis for the number of subjects to be enrolled, the statistical plan for analyzing at least the primary hypothesis, matrix showing procedure plan for each study visit, data safety monitoring plan (4 pages maximum)

We will be conducting a small clinical trial to test the safety and feasibility of a currently commercially available transcutaneous electrical nerve stimulator (TENS 7000) for treatment of delayed ejaculation.

This will involve enrollment of up to 12 men with a diagnosis delayed ejaculation. This number was chosen as the purpose of the study is to test the safety and feasibility of transcutaneous electrical stimulation of the penile nerves. Once an initial trial has been conducted, it would be expanded to more individuals for more robust statistical analysis. Our inclusion criteria are: men >18 years old and sexually active. Our exclusion criteria are: men <18 years old, not sexually active.

Due to the trial size (up to 12 men) to test safety and feasibility, we will not be able to perform a full statistical analysis but will rather be able to have men fill out a validated questionnaire on sexual function which encompasses questions that assess ejaculation.

Subjects will be contacted via chart review at Stanford Healthcare as the single site involved in the study (phone script has been included in the IRB protocol). Many have already expressed willingness to participate including men who were enrolled in the original pilot study. Willing individuals will present to the urology clinic at Stanford at an assigned date and time. They will then be interviewed in a private clinic room with one of the trial staff. This interview will consist of outlining the study purpose and protocol, reviewing the consent form, and teaching on use of the device. After this is done, if they are interested in proceeding, they can sign the consent form and take it home to consider it more. Contact numbers will be provided at that visit. We will also provide them with a link to the Qualtrics survey to take before proceeding. After this visit, no further in person visits will be required. If they have any questions, they will be able to call the number provided. If they experience any adverse events, they will be instructed to contact us immediately.

Use of the device will be explained at their one and only in person clinic visit. They will be provided with a transcutaneous electrical nerve stimulator (TENS 7000) and shown how to use it as well as the range of settings for its use in DE. They will be shown how to apply the device to the penis. Participants will be able to use the device prior to sexual activity (immediately before sexual encounter for 10 minutes or daily for up to 14 days prior) to “prime” their system or during sexual activity. Each participant will use the device these three separate ways for 6 weeks each (total of 12 weeks of use).

Participants will have 12 weeks to use the device with follow up at each 6 week point filling out the same questionnaire via Qualtrics they filling out prior to beginning the study to quantify sexual and ejaculatory function.

The primary outcome is subjective improvement in the participants perception of their DE. Secondary outcomes will be assessed via the validated questionnaire International Index of Erectile Function (IIEF) which contains questions pertaining to ejaculation and sexual satisfaction.

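### Section 8 names only the TENS 7000 and leaves out the new wearable of Section 7, and no stated outcome asks whether that wearable is usable and tolerable

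*Protocol*

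**What the plan says.** Section 7 of the protocol reports a pilot in 14 men who wore TENS pads driven by a TENS 7000. It records that "64% of men reported problems with using the TENS pads on the penis which limited use". It continues: "Using the feedback, we designed a unique wearable to continue this project based". On how the new item works, it says "The device is connected to the TENS unit leads and uses conductive rubber to apply current directly to the skin", and on what it replaces, "Instead of TENS pads there are two sets of conductive rubber tubes which pass current to stimulate penile nerves".

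Section 8 states the purpose as to "test the safety and feasibility of a currently commercially available transcutaneous electrical nerve stimulator (TENS 7000") in delayed ejaculation. On supply it says "They will be provided with a transcutaneous electrical nerve stimulator (TENS 7000) and shown how to use it", and then that men are shown how to apply the device to the penis. The words wearable, rubber and tube do not occur in Section 8.

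Section 8 gives the primary outcome as the participant's own view of whether his condition improved, with secondary outcomes from the IIEF. Follow-up at each 6-week point uses the same online questionnaire as before the study, described as quantifying sexual and ejaculatory function. For safety, men are told to contact the team if an adverse event occurs.

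**The concern.** The wearable is what distinguishes this study from the pilot. It is the part in contact with the skin, and it was built because the pads limited use. A trial whose purpose is safety and feasibility should name that part in its objective and ask the participants about it. Section 8 does neither.

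Two things are at stake. First, a favourable result, read from Section 8 alone, would be credited to a marketed stimulator, with nothing to tell the reader which skin interface was worn. Second, the trial could end with good data on sexual function and no systematic data on whether men could use and tolerate the wearable, which is the question the pilot left open.

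**Working it through.** No sample-size or power figure is involved. The check sets the sections side by side, followed by some arithmetic on what the pilot's 64% can support.

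**1. The article under test**

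| Place | What is named |
|---|---|
| Section 5 (aim) | The stimulation approach; no product |
| Section 7 (pilot) | TENS 7000 with pads |
| Section 7 (next study) | Wearable with rubber tubes, fed from the TENS unit leads |
| Section 8 (purpose) | TENS 7000; the sample-size rationale just after it names the stimulation approach |
| Section 8 (supply) | TENS 7000 only |
| Section 8 (teaching) | The device, not further defined |
| Section 9 | A device |

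In Section 7's account of the new design, the device is the wearable. In Section 8 the only article named before it is the TENS 7000. The same word therefore has two possible referents.

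**2. Signs that Section 8 was only partly updated**

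Section 7 gives two modes of use: "Rather the device will be used either before sex or daily (2 arms to the next proposed pilot study"). It adds that the wearable's size will keep most men from using it during intercourse. Section 8 allows use during sexual activity and has three modes of 6 weeks each in a total of 12 weeks. Three modes: 3 × 6 = 18 weeks. Two modes: 2 × 6 = 12 weeks. These passages contradict each other and must be reconciled; which schedule is intended is for the investigators to say. Here they serve only to show that the missing wearable is not an isolated slip.

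**3. What is measured**

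- Perceived improvement in delayed ejaculation: an efficacy outcome.
- IIEF: sexual function and satisfaction.
- Follow-up survey: the same instrument as before any use of the device in this study. A questionnaire answered before use cannot sensibly ask about comfort or problems with the wearable, and repeating it unchanged adds no such question.
- Adverse events: reported only if the participant makes contact.

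The pilot did ask about device use and comfort (Section 7). Section 8 mentions no such questions.

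**4. What the pilot's 64% can support**

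- Reproduction: 9/14 = 64.3%, which agrees with the stated 64%.
- Exact (Clopper-Pearson) 95% interval for 9/14: 35% to 87%.
- Illustration with 12 men: 3/12 = 25%, exact interval 5.5% to 57.2%; 4/12 = 33%, exact interval 9.9% to 65.1%.
- If 64% were a known constant, 3/12 would exclude it: P(X ≤ 3 | n = 12, p = 9/14) = 0.0065.
- It is not a constant. Comparing 3/12 with 9/14 by Fisher's exact test gives a two-sided p of 0.062. At a true pad rate of 35%, near the pilot's lower limit, the chance of 3 or fewer in 12 is about 34%.

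**The case against.** The strongest reply is that nothing contradictory is being tested. The wearable runs from the TENS unit leads, so the stimulator remains part of the system. Section 5, and Section 8's own reason for the sample size, state the aim as the stimulation approach and not a product. A stimulator box is not applied to the penis, so the teaching sentence in Section 8, read with Section 7, most naturally covers the wearable. Section 8 never mentions pads either.

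Most of this stands. A reader might infer that Section 8 tests the wrong article, or that Sections 7 and 8 define different interventions. The documents do not support that: Section 8 is incomplete, but it does not name a rival device. A reader might also infer that 12 men suffice to show the wearable better than pads, for instance by requiring 3 or fewer with problems. That fails as well. The pilot rate is uncertain, enrolment is up to 12, Section 8 says willing candidates include men from the pilot, so the samples may overlap, and the pilot included use during intercourse, which Section 7 says the wearable mostly prevents.

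It can also be said that the full questionnaire is not shown and that reporting detail belongs in a statistical analysis plan. The second point is fair for the choice of interval. It does not reach the main gap: which questions are put to participants is protocol content, and Section 8 specifies the pre-use questionnaire again. The request for self-reported adverse events does cover part of safety, but it gives no systematic count of men who found the wearable hard to use.

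**Conclusion.** The point holds as an omission in Section 8, together with a gap in measurement. The objective and supply sentences identify the intervention incompletely, and no stated outcome or survey covers the usability and tolerability of the new skin interface beyond adverse events that men choose to report.

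No number, outcome or analysis in the protocol is wrong because of this. The rewording alone would be close to clerical. What makes the point worth acting on is that a stated purpose, feasibility, goes unmeasured for the component that was changed, and that a few questions would correct it.

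The conclusion assumes that this trial uses the wearable, as Section 7 says, and that the follow-up questionnaire is unchanged from baseline, as Section 8 says. If device questions already exist in the online survey, only the wording needs attention.

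**What to change.** 1. Reconcile Section 8 with Section 7: in the objective and supply sentences, name the TENS 7000 together with the conductive-rubber wearable, and define the device once.
2. Limit the safety and feasibility conclusions to that system.
3. Add the pilot's device-use and comfort questions to the week-6 and week-12 surveys.
4. Report the number and proportion of men with problems, with an exact 95% confidence interval. With at most 12 men it will be wide (3/12 would give 5.5% to 57.2%), and the text should say so.
5. If the pilot is mentioned, show 9/14 with its interval of 35% to 87% as description only, with no test and no pass mark, and state how many participants also took part in the pilot.

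The cost is a protocol wording change and a few more survey items, reusing questions the investigators already have. The drawback is a narrower safety claim.

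### A trial of the safety and feasibility of a new wearable electrode schedules no contact around first use and none after use ends

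*Protocol*

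**What the plan says.** Section 8 states the purpose: "We will be conducting a small clinical trial to test the safety and feasibility". On size it says: "This will involve enrollment of up to 12 men with a diagnosis delayed ejaculation".

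Section 7 reports a pilot of 14 men with adhesive pads, in which "64% of men reported problems with using the TENS pads on the penis which limited use". It then introduces a replacement: "Using the feedback, we designed a unique wearable to continue this project based". The change is to the part that touches the skin: "Instead of TENS pads there are two sets of conductive rubber tubes which pass current to stimulate penile nerves". No earlier use of this wearable is described.

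On contact with participants, section 8 says: "Use of the device will be explained at their one and only in person clinic visit". Men are shown how to apply the device at that visit; a supervised first use is not mentioned. Then: "After this visit, no further in person visits will be required". Follow-up is remote: "Participants will have 12 weeks to use the device with follow up at each 6 week point". The instrument is the same Qualtrics questionnaire as at baseline, and its stated purpose is to quantify sexual function and ejaculation. Separately, men receive contact numbers and are told to get in touch immediately if an adverse event occurs.

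**The concern.** Section 7 presents the wearable as the answer to the pilot's difficulties with pads. Whether it fits, stays in place and is tolerated on the skin is therefore a main question for this trial, alongside safety. The schedule leaves two periods uncovered: the first weeks of use, and everything after the last use.

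In both periods information reaches the team only if a man decides to call. With up to 12 men and no comparison group, the report will depend heavily on what was not reported. If nobody was asked, no reports may mean no problems, or problems that men put up with, or men who quietly stopped using the device. The trial also could not say systematically whether a local problem cleared or first appeared after use stopped. Section 8 expects a larger trial to follow, which would start from these gaps.

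**Working it through.** **Timing of scheduled contact (Protocol section 8)**

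- Before use: one clinic visit and the baseline questionnaire. Neither can observe an effect of use.
- First scheduled contact after use starts: 6 weeks × 7 = 42 days.
- Stated duration: 12 weeks, so contacts at weeks 6 and 12, which is 2 per man and at most 2 × 12 = 24 questionnaires.

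**When use ends.** The stated 12 weeks does not follow from section 8's own description, which has three ways of use for 6 weeks each: 3 × 6 = 18. Section 7 describes two ways: 2 × 6 = 12. The readings are:

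| Reading | Use ends | Last scheduled contact | Scheduled observation after last use |
|---|---|---|---|
| Two ways, 12 weeks | week 12 | week 12 | 0 weeks |
| Three ways, 18 weeks, follow-up continues | week 18 | week 18 | 0 weeks |
| Three ways, 18 weeks, follow-up stops at stated total | week 18 | week 12 | none; last contact is 6 weeks before use ends |

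The conclusion is the same in every row.

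**What the scheduled contacts ask.** The follow-up questionnaire is the baseline one. Since it is first completed before any use, it has no evident reason to contain device questions, and none is described. Moving it earlier or later would not by itself detect a local problem, so a remedy has to change content as well as timing.

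**How much reliance on volunteered reports could matter.** The protocol states no event rate, so this is illustration only. Let p be the true proportion of men harmed and s the proportion of those who volunteer it. The chance of hearing of at least one case in 12 men is 1 − (1 − p·s)^12.

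- p = 10%, everyone asked (s = 1): 1 − 0.90^12 = 71.8%
- p = 10%, s = 0.8: 1 − 0.92^12 = 63.2%
- p = 10%, s = 0.5: 1 − 0.95^12 = 46.0%
- p = 10%, s = 0.3: 1 − 0.97^12 = 30.6%

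With full ascertainment, no events in 12 men gives a one-sided 95% upper limit of 1 − 0.05^(1/12) = 22.1%. If s were 0.5, the same silence would exclude only rates above 22.1% / 0.5 = 44.2%. The values of p and s are assumptions.

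**The case against.** The strongest reply is that a reporting route exists. Men are told to make contact immediately, they hold the numbers, and no end date is set. A reader might infer that the final safety statement will rest only on 6-week recall of the period on the device. The text does not support that: volunteered reports are made in real time and could come after use ends. What remains is that this route is passive, so it can show harm but cannot show its absence.

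A second reply is that the device is less novel than it sounds. The stimulator is the same commercial unit as in the pilot, used with a similar range of settings, and section 7 says similar technology is sold online. This stands. The novelty lies in the skin interface and the fit, which is where the pilot met difficulty.

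Third, a reader might carry the pilot's 64% over to the wearable, or expect most problems to show in the first week. Neither is supported. The 64% concerns difficulty using pads, not harm; no onset times are given; the pilot covered three modes of 6 weeks each; and the wearable was redesigned to address that feedback. Nor do the documents support a count of home sessions before the first contact. Such a count would need men to start together and to use the daily mode first without a break, whereas section 8 brings men in individually and limits daily priming to as many as 14 days before sexual activity.

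Finally, the institutional review board protocol that section 8 mentions is not shown and may contain more. That is a reason to check it and then bring this document into line.

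**Conclusion.** The point holds in limited form. On any reading of section 8, no contact is scheduled in the first 42 days of use or after last use, and the contacts that are scheduled have no stated question about device problems. The instruction to report adverse events softens this but does not close the gap.

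The conclusion rests on the schedule alone and needs no assumed rate. The fall from 71.8% to 46.0% shows scale under a 10% harm rate and half of events volunteered; over the range of 30% to 80% volunteered, the figure runs from 30.6% to 63.2%. It is not an estimate for this device. The documents do not show that harm is likely early, late or lasting, and they do not make the trial's efficacy questionnaires unusable. The change is worth making before enrolment because it is cheap and bears directly on the trial's stated purpose.

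**What to change.** In section 8:

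1. Add a short online or telephone check about one week after each man's first actual use, asking about fit, skin or other local problems, and whether and how he has used the device. Count from first use, not from the clinic visit, because a man using it only before sex may not have begun within a week of the visit.
2. Add one remote survey some weeks after last use (for example 6), asking whether any problem persists or has newly appeared.
3. Reconcile the three ways of use for 6 weeks each with the stated 12-week total, and both with the two ways of use in section 7, so that last use is a defined date from which item 2 can be counted. Which description is right is for the investigators to settle.

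Keep the instruction to report adverse events immediately; these contacts supplement it.

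The cost is two short remote contacts for each of up to 12 men, 2 × 12 = 24 in all, and a somewhat longer follow-up. Both surveys can use the Qualtrics system already planned, and neither needs a clinic visit.

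### The protocol conflicts on whether the device is used during sex; if such use is in the trial or remains possible, its adverse-event reporting does not reach partners

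*Protocol*

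**What the plan says.** On the way the device is used, the protocol says different things in different sections.

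- Section 5 hypothesises that stimulation "either before or during sexual activity, will reduce ejaculatory latency time". Section 6 repeats the before-or-during wording.
- Section 8 allows use ahead of sexual activity to prime "their system or during sexual activity", and then states: "Each participant will use the device these three separate ways for 6 weeks each (total of 12 weeks of use").
- Section 7, describing the redesigned wearable, says: "The size of the device will prevent most men from using the device during intercourse". The next sentence reads: "Rather the device will be used either before sex or daily (2 arms to the next proposed pilot study").

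Section 7 also describes the electrode: the device "uses conductive rubber to apply current directly to the skin".

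On safety, Section 5 opens with "The aim of this clinical trial is to test the safety and feasibility". The only adverse-event text is in Section 8: "If they experience any adverse events, they will be instructed to contact us immediately". After the single clinic visit there are no further in-person visits. Follow-up at each 6-week point is the same online questionnaire that was completed at baseline, described as measuring sexual and ejaculatory function. Partners are not mentioned in connection with exposure, reporting or consent.

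**The concern.** A trial whose first aim is safety has to say whose safety it observes. If a man wears a current-carrying electrode during partnered sex, his partner may also be exposed. A reporting instruction limited to what the participant experiences, together with a questionnaire on his own sexual function, would not pick up an effect on the partner except by chance. The trial could then report no device-related harm when harm to partners had never been asked about. A partner's discomfort is also a plausible reason for a man to stop using the device, so the same gap touches feasibility.

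All of this depends on whether use during sex is part of the trial, and the protocol does not settle that.

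**Working it through.** **Step 1. Which ways of use does the stated duration fit?** Inputs: 6 weeks per way of use and a 12-week total (Section 8); three ways of use (Section 8); two ways of use (Section 7).

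Weeks needed = ways of use x 6.

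| Source of the number of ways | Ways | Weeks needed | Stated total |
|---|---|---|---|
| Section 8 | 3 | 3 x 6 = 18 | 12 |
| Section 7 | 2 | 2 x 6 = 12 | 12 |

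Section 8's own inputs do not reproduce its 12 weeks; Section 7's do. On the stated total there is no 6-week period left for a third way of use. Yet Section 8 and the hypotheses in Sections 5 and 6 still include use during sexual activity. The arithmetic shows a conflict and cannot show which text is intended.

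**Step 2. Does Section 7 close off use during sex?** It plans use before sex or daily, which points away from it. But its remark on size concerns most men, not all, and concerns intercourse, a narrower term than the sexual activity of Section 8. No sentence in the protocol prohibits use during sex. So even on the two-way reading, the possibility remains for some men.

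**Step 3. Would a partner be exposed?** The electrode is conductive rubber carrying current to the skin of the penis (Section 7). Section 6 frames the expected benefit in terms of intravaginal latency, which implies partnered intercourse. Contact by a partner is therefore plausible. It is not stated. Sexual activity is not defined, and the protocol does not say whether any conductive surface faces outward when the device is worn. Section 8 itself names only the TENS 7000 and the device; the rubber electrode is described in Section 7.

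**Step 4. Would a partner effect be recorded?** Setting the reporting instruction beside the follow-up plan:

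- Spontaneous reporting: limited to adverse events the participants themselves experience.
- Scheduled follow-up: the baseline questionnaire repeated at weeks 6 and 12, described as covering sexual and ejaculatory function.
- Visits: none after the first.

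No route described in this document asks about a partner.

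**The case against.** The strongest reply is that the premise may be false. Section 7 states in plain terms how this device is to be used, the 12-week total agrees with it, and the earlier pilot did use three ways for 6 weeks each, so the three-way wording in Section 8 may have been carried over. If reconciliation removes use during sex and rules it out for every man, the partner question largely disappears. This stands, and it is why the point is conditional. It does not dispose of the point: the sponsor could equally resolve the count by lengthening the schedule, which would leave the exposure in place.

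A second reply is that the gap is read from silence. Consent pages are not in the text at hand, and Section 8 mentions a separate IRB protocol; warnings to partners or a reporting route may be there. This also stands. The finding can be made only about this protocol.

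A third is that participants' own adverse events are collected only by spontaneous report, so a partner item alone would be an odd priority. That is fair, and the survey item proposed below therefore asks about both.

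Two stronger readings are tempting and should be resisted. A reader might infer that the plan definitely brings partners into contact with a live electrode; no sentence says so. A reader might also infer that up to 12 partners, one per man, would be exposed, and attach a probability of at least one event. Section 7 says most men could not use the device during intercourse. If most means more than half, at least 7 of 12 could not, leaving at most 12 - 7 = 5 who could. The documents give no rate of partner effects, so any such probability would rest on an invented figure.

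**Conclusion.** The point holds in a limited, conditional form. What is firm is that Sections 5, 6 and 8 include use during sexual activity, Section 7 plans without it, and the duration fits two ways of use and not three. It is equally firm that the reporting instruction and follow-up described in this protocol do not reach partners.

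What follows is conditional on use during sex being allowed or remaining possible, on the inference that a partner may then touch the electrode, and on there being no partner provision in the consent form or IRB protocol. Under those conditions the trial's safety conclusion could not speak to partner effects. The consequence is a limit on what can be concluded. No frequency of harm can be put on it from the documents.

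**What to change.** 1. Reconcile Sections 7 and 8, and the hypotheses in Sections 5 and 6, on whether use during sexual activity is part of this trial, and make the number of ways of use and the total weeks agree. Which text is right is for the sponsor to decide.
2. If any such use is allowed or possible:
   - extend the reporting instruction to adverse events in the participant or his partner;
   - add one item to the week-6 and week-12 surveys asking whether the device was used during sexual activity and whether the participant or partner had any effect from it;
   - report partner effects separately from participants' own.
3. If partner effects are not to be collected, state that the safety conclusion does not cover partners.
4. If the consent form or IRB protocol already provides for partners, a cross-reference in Section 8 is enough for whatever it covers.

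The cost is a few words in the instruction and one survey item. The downside is that partner information would come second-hand through the participant, and collecting it needs a line in the ethics submission.
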